17.4 Secondary endpoints

17.4.1 Supportive secondary endpoints

17.4.1.1 Efficacy endpoints

Time from randomisation to HbA_{1c} > 6.5% at 2 consecutive visits from week 26.

Time from randomisation to HbA_{1c} > 6.5% at 2 consecutive visits from week 26 (including week 26 if HbA_{1c} was ≥ 6.5% at week 12).will be analysed and presented in the same way as the primary endpoint.

HbA_{1c}

Change from baseline in HbA_{1c} after 26 weeks of treatment will be analysed using the standard MMRM model.

Body weight

Change from baseline in body weight after 26 and 104 weeks of treatment will be analysed using the standard MMRM model.

Insulin dose after 26 and 104 weeks of treatment

The actual insulin dose will be summarised descriptively according to regimen as dose in units, and units/kg. The actual daily insulin dose will be analysed using the standard MMRM model.

HbA_{1c} responder after 26 and 104 weeks of treatment (yes/no)

Two dichotomous endpoints (responder/non-responder) will be defined based on whether a subject has met a specific target level after 26 and 104 weeks of treatment:

- HbA_{1c} target < 7.0%⁷
- HbA_{1c} target ≤ 6.5%²⁷

Analysis of each of the four responder endpoints will be based on a logistic regression model with treatment, HbA_{1c} group, previous OAD treatment and region as fixed factors and baseline HbA_{1c} value as a covariate. Subjects withdrawing from the trial or discontinuing treatment will be imputed as being non-responder from time of withdrawal/discontinuation in line with the evaluation of the primary endpoint.

HbA_{1c} responder endpoints without weight gain

Responder for HbA_{1c} without weight gain after 26 and 104 weeks of treatment will be defined as HbA_{1c} < 7.0% or ≤ 6.5% and change in body weight from baseline ≤ 0. Analysis of each of the 2 responder endpoints will be based on a logistic regression model with treatment, HbA_{1c} group, previous OAD treatment and region as fixed factors and baseline HbA_{1c} and baseline body weight as covariates. Subjects withdrawing from the trial or discontinuing treatment will be imputed as being non-responder from time of withdrawal/discontinuation in line with the evaluation of the primary endpoint.

HbA_{1c} responder endpoints without treatment-emergent severe or BG confirmed symptomatic hypoglycaemic episodes

Responder for HbA_{1c} without treatment-emergent severe or BG confirmed symptomatic hypoglycaemic episodes after 26 and 104 weeks of treatment will be defined as HbA_{1c} < 7.0% or ≤ 6.5% and without treatment-emergent severe or BG confirmed symptomatic hypoglycaemic episodes during the last 12 weeks of each treatment period. Analysis of each of the 2 responder endpoints will be based on a logistic regression model with treatment, HbA_{1c} group, previous OAD treatment and region as fixed factors and baseline HbA_{1c} values as a covariate. Subjects withdrawing from the trial or discontinuing treatment will be imputed as being non-responder from time of withdrawal/discontinuation in line with the evaluation of the primary endpoint.

HbA_{1c} responder endpoints without treatment-emergent severe or BG confirmed symptomatic hypoglycaemic episodes and without weight gain

Responder for HbA_{1c} without treatment-emergent severe or BG confirmed symptomatic hypoglycaemic episodes and without weight gain after 26 and 104 weeks of treatment will be defined as HbA_{1c} <7.0% or ≤6.5% without treatment-emergent severe or BG confirmed symptomatic during the last 12 weeks of each treatment period, and change in body weight from baseline ≤ 0. Analysis of each of the 2 responder endpoints will be based on a logistic regression model with treatment, HbA_{1c} group, previous OAD treatment and region as fixed factors and baseline HbA_{1c} values and baseline body weight as covariates. Subjects withdrawing from the trial or discontinuing treatment will be imputed as being non-responder from time of withdrawal/discontinuation in line with the evaluation of the primary endpoint.

Fasting plasma glucose

Change from baseline in FPG after 26 and 104 weeks of treatment will be analysed using the standard MMRM model.

9-point profile

The following 6 endpoints from the 9-point SMPG profile will be defined:

- 9-point profile (individual points in the profile)
- Mean of the 9-point profile, defined as the area under the profile (calculated using the trapezoidal method) divided by the measurement time
- Prandial plasma glucose increments (from before meal to 90 min after for breakfast, lunch and dinner). The mean increment over all meals will be derived as the mean of all available meal increments

A MMRM will be fitted to the 9-point profile data where measurements within subjects will be assumed correlated using an unstructured residual covariance matrix. The model will include treatment, visit, time, region and treatment by time interaction as fixed factors and baseline value corresponding to each time as covariate. Interactions between visit and all factors and covariates are also being included in the model.

Change from baseline in mean of the 9-point profile and prandial increment endpoints will be analysed separately using the standard MMRM model.

Blood pressure (systolic and diastolic)

Change from baseline in systolic and diastolic blood pressure will be analysed separately using the standard MMRM model.

Fasting C-peptide and fasting human insulin

These endpoints will be analysed separately using the standard MMRM model.

Fasting lipid profile

Cholesterol, LDL cholesterol, HDL cholesterol, VLDL cholesterol, triglycerides and free fatty acids will be analysed separately using the standard MMRM model. In these statistical analyses, the endpoint will be log-transformed and so will the corresponding baseline covariate.

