6.2 Inclusion criteria

For an eligible subject, all inclusion criteria must be answered "yes".

1. Informed consent obtained before any trial-related activities. Trial-related activities are any procedures that are carried out as part of the trial, including activities to determine suitability for the trial
2. Male or female, age ≥ 18 years at the time of signing informed consent
3. Subjects diagnosed (clinically) with type 2 diabetes mellitus prior to the day of screening
4. HbA_{1c} 7.0–11.0% (both inclusive) (53–97 mmol/mol) by central laboratory analysis
5. Body mass index (BMI) ≥ 20 kg/m²
6. Insulin naïve subjects; however short term insulin treatment for a maximum of 14 days prior to the day of screening is allowed, as is prior insulin treatment for gestational diabetes
7. Stable daily dose(s) including any of the following antidiabetic drug(s)/regimens within 90 days prior to the day of screening:
 - Biguanides (metformin ≥ 1500 mg or maximum tolerated dose documented in the subject medical record)
 - Other OAD(s) allowed: sulphonylurea, glinides, pioglitazone, and DPP4-inhibitors (\geq half of the maximum approved dose according to local label or maximum tolerated dose as documented in subject medical record)

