8.1.4 Treatment initiation and titration

To optimise and maintain glycaemic control, the investigator should throughout the trial be in contact with the subject every 3rd month. After randomisation there will be a phone contact after 1 week and visits to the site after 2 and 4 weeks to assist the subjects in initiating the new treatment.

Treatment regimen

All subjects will start on 10 dose steps (10 units of IDeg and 0.36 mg of liraglutide) or 10 units of IGlar QD. Maximum dose for IDegLira is 50 dose steps (50 units of IDeg and 1.8 mg of liraglutide). There is no predefined maximum dose of IGlar.

Injection area

IDegLira or IGlar should be injected s.c. into the thigh, upper arm (deltoid area) or the abdomen. It is recommended that the chosen region is the same throughout the trial. Rotation of injection sites within a given region is preferable.

Time of injection

IDegLira or IGlar should be injected QD at any time of the day, but preferably at the same time of day throughout the trial.

Titration

Dose will be adjusted twice weekly by the subject 3-4 days apart. The investigator will evaluate the diary and prescribe dose at all contacts.

Titration should be performed based on the mean of 3 pre-breakfast SMPG values, measured on the day of the titration and the 2 previous days. Titration should preferably be performed on the same days of the week throughout the trial (E.g., Mondays and Thursdays). The dose adjustment will be performed according to [Table 8-1](#).

Table 8-1 Twice weekly titration algorithm for trial products

Mean of 3 pre-breakfast plasma glucose mmol/L (mg/dL)	Twice weekly adjustments: IDegLira (dose steps) IGlar (units)
< 4.0 (< 72)	-2
4.0-5.0 (72-90)	No adjustment
> 5.0 (> 90)	+2

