Investigators working on the trial may use their own electronic systems to capture source data.

17 Statistical considerations

Novo Nordisk will analyse and report data from all sites together.

All analyses of efficacy and safety endpoints will be based on the full analysis set (FAS).

All efficacy endpoints and PRO endpoints will be summarised using the FAS and safety endpoints will be summarised using the safety analysis set (SAS).

The impact of protocol deviations and outliers may be investigated further in sensitivity analyses if deemed relevant.

Unless otherwise specified, all continuous measurements will be summarised descriptively at each visit by treatment using observed data. Endpoints that are analysed untransformed and endpoints that are not formally analysed are summarised by the arithmetic mean, standard deviation, median, and minimum and maximum value. Endpoints that are analysed log-transformed are supplemented with the geometric mean and coefficient of variation. For measurements over time, mean values will be plotted to explore the trajectory over time. Observed data will be used as the basis for plotting data if not otherwise specified. Change from baseline plots will be based on Least Square Means and SEs estimated from the mixed model for repeated measurement (MMRM). For endpoints that are analysed log-transformed, the geometric mean values will be plotted. In addition, plots will be made showing mean curves by time of treatment discontinuation. All descriptive summaries and plots will be based on on-treatment data unless otherwise specified.

Only endpoints derived after 26 and 104 weeks of treatment will be analysed statistically.

Subjects withdrawing from the trial or discontinuing treatment will contribute to the primary analysis as needing rescue therapy from the time of withdrawal/discontinuation.

For secondary endpoints, the expected percentage of missing data after 26 weeks of treatment is around 5%. Due to the nature of the trial design, the expected percentage of missing data after 104 weeks of treatment is 40% and 60% for IDegLira and IGlar respectively.

If an assessment has been made both at screening and randomisation, and if not otherwise specified, the value from the randomisation visit will be used as the baseline value. If the value measured at the randomisation visit is missing and the assessment also has been made at screening, then the screening value will be used as the baseline value.

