Laboratory values below the lower limit of quantification (LLOQ) will be set to $\frac{1}{2}\text{LLOQ}$.

A MMRM with an unstructured covariance matrix, with testing performed at week 26 and 104 will be applied for secondary continuous endpoints. The model includes treatment, visit, HbA_{1c} group, pre-trial diabetes medication and region as fixed factors and the corresponding baseline value as a

covariate. Interactions between visit and all factors and the covariate are also to be included in the model.

The factor “baseline HbA_{1c} group” is a dichotomised baseline HbA_{1c} variable with 2 categories: HbA_{1c} <8.5% or HbA_{1c} ≥8.5%.

The factor “previous OAD treatment” has 2 levels: OAD(s) + sulphonylurea or OAD(s).

The factor “region” has 5 levels: Europe (Norway, Israel, Russia, Turkey, Italy, UK, Slovakia, Hungary, Czech Republic and Poland), North America (US), South America (Mexico, Brazil and Argentina), Africa (South Africa), and Asia (India).

In the following, this model will be referred to as the standard MMRM model. This analysis will estimate the difference in change from baseline in the endpoint between IDegLira and IGlar assuming that subjects remain on trial product until week 26 and 104, respectively. In this model it is assumed that data are missing at random which is a reasonable assumption since most missing data will arise from subjects withdrawing due to inadequate glucose control as observed at the time of withdrawal.

Presentation of results from a statistical analysis will include the estimated mean treatment effects (Least Square Means) for absolute values and change from baseline. In addition, estimated mean treatment difference (or ratio) will be presented together with the two-sided 95% confidence interval and corresponding two-sided p-value.

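### The insulin-dose MMRM adjusts for a baseline dose that is constant, or nearly so, in insulin-naive subjects, so its only covariate does no work and some precision is lost

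*Protocol*

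**What the plan says.** Insulin dose after 26 and 104 weeks is a supportive secondary efficacy endpoint (Protocol 4.2.2.1). The week-26 version carries the asterisk for endpoints selected for disclosure. Section 17.4.1.1 gives the analysis: "The actual insulin dose will be summarised descriptively according to regimen as dose in units, and units/kg", and then "The actual daily insulin dose will be analysed using the standard MMRM model". It makes no exception for this endpoint.

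Section 17 defines the standard MMRM. The factors are treatment, visit, HbA1c group, "pre-trial diabetes medication and region as fixed factors and the corresponding baseline value as a" covariate. It adds: "Interactions between visit and all factors and the covariate are also to be included in the model". For an assessment made at both screening and randomisation, "the value from the randomisation visit will be used as the baseline value".

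Inclusion criterion 6 in section 6.2 reads: "Insulin naïve subjects; however short term insulin treatment for a maximum of 14 days prior to the day of screening is allowed", with a further allowance for past gestational diabetes. Section 8.1.4 sets the start of treatment: "All subjects will start on 10 dose steps (10 units of IDeg and 0.36 mg of liraglutide) or 10 units of IGlar QD". Amendments 1 to 4 leave the insulin-dose model as it is.

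**The concern.** The covariate in an MMRM of this kind is there to remove between-subject variation that was present before treatment. For HbA1c, body weight, FPG and the other continuous endpoints sent to this model, the baseline value is measured and varies between subjects. For insulin dose it does not. The prescribed covariate is then the same number for everyone, or for nearly everyone, and nothing in the text takes its place.

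What is at stake is the width of the confidence interval for the dose difference. A plausible prognostic covariate, baseline body weight, is already measured fasting at visit 2. The protocol already uses it as a covariate in the responder models that require no weight gain (section 17.4.1.1), but not here.

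**Working it through.** **Plan's own figure.** The protocol gives no variance, effect size or precision target for insulin dose. Its only sizing figure is 90% power for the primary log-rank test (section 17.1). With 500 × (0.45 + 0.55) = 500 events and HR = ln(0.55)/ln(0.45) = 0.749, the Schoenfeld formula gives power = Φ(√500/2 × |ln 0.749| − 1.96) ≈ 89.9%. That reproduces, but it has no bearing on this endpoint.

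**Step 1: what baseline dose can be.**
- Dose before treatment (sections 6.2 and 17): 0. The possible exception is a subject who had short-term insulin before screening and is given a non-zero value.
- First trial dose (section 8.1.4): 10 units or 10 dose steps in both arms. It is also taken after randomisation, so it is not strictly a baseline.

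**Step 2: rank of the fixed-effect design.** Take the two tested visits, weeks 26 and 104, with every term crossed with visit. Per visit there are 1 intercept, 1 treatment, 1 HbA1c group, 1 prior medication and 4 region columns (5 regions), which makes 8. Two visits give 16 columns. A covariate adds one column per visit, so 18.

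| Covariate | Columns | Rank |
|---|---|---|
| none | 16 | 16 |
| baseline dose, all 0 | 18 | 16 |
| start dose, all 10 | 18 | 16 |
| baseline body weight | 18 | 18 |

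A column of zeros carries nothing, and a column of tens is ten times the intercept at each visit. Both covariate columns are therefore inestimable. If 1%, 2% or 5% of subjects are given a non-zero baseline, the rank rises to 18, but the slope then rests on those few subjects and can explain very little.

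**Step 3: effect on the treatment estimate.** In one simulated data set of 1,000 subjects at a single visit, with invented dose and weight values, the treatment estimate was −10.35 (SE 1.256) without a covariate. It was the same with a baseline of 0 for all and with 10 for all. Adding weight gave −10.54 (SE 1.130).

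**Step 4: what weight could gain.** If r is the partial correlation of dose with baseline weight given the other model terms, the SE is multiplied by √(1 − r²). The protocol does not state r, so the values below are assumptions.

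| r | √(1 − r²) | Interval narrower by |
|---|---|---|
| 0.2 | 0.980 | 2% |
| 0.3 | 0.954 | 5% |
| 0.4 | 0.917 | 8% |
| 0.5 | 0.866 | 13% |

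The simulation agrees with the formula. Its weight effect had SD 0.5 × 18 = 9 against residual SD 18, so r = 9/√(81 + 324) = 0.447 and the expected ratio is 0.894. The observed ratio was 1.130/1.256 = 0.900.

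**The case against.** The strongest reply is that the term simply does not apply. The endpoint is a dose level, not a change from baseline, and the flow chart has no insulin-dose assessment at visits 1 or 2. There is thus no baseline value to enter, software drops the aliased columns, and the SAP, which is not at hand, may say so. On this view, wanting body weight is only a preference among valid models.

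Much of this stands. The comparison is valid with or without the dead term, and omitting a prognostic covariate is not an error in itself. What remains is that the protocol sends this endpoint to a model whose one covariate cannot work, although it tailors covariates for the responder, lipid and 9-point-profile analyses.

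Several stronger readings are tempting, and the protocol does not support them:
- **The model fails or the result is biased.** Step 3 shows otherwise.
- **The endpoint is analysed unadjusted.** HbA1c group, pre-trial medication and region remain, each crossed with visit.
- **Baseline dose is zero for every subject.** Criterion 6 allows up to 14 days of insulin before screening, so constant or nearly so is as far as the text goes.
- **A confirmatory result is at risk.** The asterisk means selected for disclosure, at week 26 only.
- **The protocol itself says dose scales with weight.** The units/kg figure is a descriptive summary and no more.

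The size is also open to challenge. The relevant r is partial, so weight variation already explained by region or the other factors must not be counted again. IDegLira is capped at 50 dose steps while IGlar has no predefined maximum, and a ceiling may flatten the dose–weight relation in that arm.

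**Conclusion.** The point holds as a minor one. As written, the insulin-dose model names a covariate that is constant or nearly so by design. If it is strictly constant, the term and its visit interaction cannot be estimated. If a few subjects differ, the term can be estimated but does almost nothing. The cost is precision alone: an interval wider by an amount that the protocol does not allow one to fix. It would be about 2% to 13% for an assumed partial correlation between 0.2 and 0.5, with the lower end more likely if the cap binds for many IDegLira subjects. No power statement or decision rule in the protocol depends on it.

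**What to change.** State in the SAP that, for daily insulin dose, the standard MMRM uses baseline body weight in place of the endpoint's own baseline value, with its visit interaction and all other factors unchanged. Continuous baseline HbA1c, also with its visit interaction, may be added as an option. Settling this before the data are analysed also avoids a later covariate choice in an open-label trial.

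The cost is one sentence and one or two extra model terms. Both variables are already collected at visit 2. The one modelling drawback is that a common weight slope across arms may fit the capped arm less well, which would reduce the gain.

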4.2.2 Secondary endpoints

4.2.2.1 Supportive secondary endpoints

Supportive secondary efficacy endpoints

- Time from randomisation to $\text{HbA}_{1c} > 6.5\%$ at 2 consecutive visits from week 26* (including week 26, if HbA_{1c} was $> 6.5\%$ at week 12)
- Change from baseline in HbA_{1c} after 26 weeks of treatment*
- Change from baseline in body weight after 26* and 104 weeks of treatment
- Insulin dose after 26* and 104 weeks of treatment
- Responder after 26 and 104 weeks of treatment (yes/no):
 - $\text{HbA}_{1c} < 7.0\%*$
 - $\text{HbA}_{1c} < 7.0\%$ without weight gain
 - $\text{HbA}_{1c} < 7.0\%$ without treatment-emergent severe or blood glucose (BG) confirmed symptomatic hypoglycaemic episodes during the last 12 weeks of treatment
 - $\text{HbA}_{1c} < 7.0\%$ without treatment-emergent severe or BG confirmed symptomatic hypoglycaemic episodes during the last 12 weeks of treatment and without weight gain
 - $\text{HbA}_{1c} \leq 6.5\%*$
 - $\text{HbA}_{1c} \leq 6.5\%$ without weight gain
 - $\text{HbA}_{1c} \leq 6.5\%$ without treatment-emergent severe or BG confirmed symptomatic hypoglycaemic episodes during the last 12 weeks of treatment
 - $\text{HbA}_{1c} \leq 6.5\%$ without treatment-emergent severe or BG confirmed symptomatic hypoglycaemic episodes during the last 12 weeks of treatment and without weight gain

- Change from baseline after 26 weeks of treatment in:
 - Fasting plasma glucose (FPG)*
 - 9-point Self-measured plasma glucose (SMPG) profile:
 - 9-point profile (individual points in the profile)*
 - Mean of the 9-point profile
 - Prandial plasma glucose increments (from before meal to 90 min after breakfast, lunch and dinner). The mean increment over all meals will be derived as the mean of all available meal increments
- Change from baseline after 104 weeks of treatment in:
 - FPG
 - 9-point SMPG profile:
 - 9-point profile (individual points in the profile)
 - Mean of the 9-point profile
 - Prandial plasma glucose increments (from before meal to 90 min after breakfast, lunch and dinner). The mean increment over all meals will be derived as the mean of all available meal increments
- Change from baseline after 26 and 104 weeks of treatment in:
 - Blood pressure (systolic and diastolic)
 - Fasting C-peptide and fasting human insulin

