 - Fasting lipid profile (cholesterol, low-density lipoprotein cholesterol [LDL cholesterol], high-density lipoprotein cholesterol [HDL cholesterol], very-low-density lipoprotein cholesterol [VLDL cholesterol], triglycerides, and free fatty acids)

Supportive secondary safety endpoints

- Number of treatment-emergent severe or BG confirmed symptomatic hypoglycaemic episodes during 26 and 104 weeks of treatment*
- Number of treatment emergent hypoglycaemic episodes according to ADA definition during 26 and 104 weeks of treatment
- Number of treatment-emergent nocturnal severe or BG confirmed symptomatic hypoglycaemic episodes during 26 and 104 weeks of treatment
- Number of treatment-emergent adverse events (TEAEs) during 26 and 104 weeks of treatment
- Change from baseline in clinical evaluation after 104 weeks of treatment:
 - Eye examination – fundus photography/dilated fundoscopy
 - Electrocardiogram (ECG)
 - Urine albumin/creatinine ratio
- Change from baseline after 26 and 104 weeks of treatment:
 - Pulse
- Change from baseline in laboratory assessments after 26 and 104 weeks of treatment:
 - Biochemistry

- Haematology
- Calcitonin

Supportive secondary health economics endpoints

- Change from baseline in patient reported outcomes (PRO) after 26 and 104 weeks of treatment:
 - Medical outcomes study 36-item short form version 2 (SF-36v2)
 - Treatment related impact measure (TRIM-D)

* Key supportive secondary endpoint prospectively selected for disclosure (e.g. clinicaltrials.gov and EudraCT)

5 Trial design

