17.3 Primary endpoint

The following endpoint will be assessed up to 104 weeks. Time from randomisation to inadequate glycaemic control and need for treatment intensification defined as an $\text{HbA}_{1c} \geq 7\%$ at 2 consecutive visits from week 26 (including week 26, if HbA_{1c} was \geq to 7% at week 12).

Subjects withdrawing from the trial or discontinuing treatment will contribute to the primary analysis as needing rescue therapy from the time of withdrawal/discontinuation. The data will inherently be interval censored, since HbA_{1c} is only measured at the scheduled visits while subjects may reach an $\text{HbA}_{1c} \geq 7.0\%$ at any time between 2 visits (including week 26 if HbA_{1c} was $>$ to 7% at week 12).

The primary endpoint will be analysed using a stratified log-rank test where treatment, baseline HbA_{1c} group and previous OAD treatment will be included as strata in the model.

The variable “baseline HbA_{1c} group” is a dichotomised baseline HbA_{1c} variable with 2 categories: $\text{HbA}_{1c} < 8.5\%$ or $\text{HbA}_{1c} \geq 8.5\%$.

The variable “previous OAD treatment” is a categorical variable with 2 categories: OAD(s) + sulphonylurea or OAD(s).

Formally, let D be the hazard ratio for time to treatment intensification. The null-hypothesis of no treatment difference will be tested against the alternative hypothesis as given by

$H_0: D = 1$ against $H_A: D \neq 1$

Kaplan-Meier curves by treatment arm and strata from the model will be presented.

Sensitivity analysis

The following two sensitivity analysis will be carried out.

The first sensitivity analysis will take the interval censored nature of the data into account by using a semi-parametric proportional hazards regression model for interval censored data. The chosen model can be viewed as an extension of Turnbull’s method²⁴ from a non-parametric model to a semi-parametric proportional hazards models as described in Alioum.²⁵

The log-likelihood function of the data under the proportional hazards assumption can be expressed as:

$\sum_{i=1, \dots, n} \log \left(\sum_{j=1, \dots, m} \mu_{ij} (S(p_{j-1})^{\exp(\beta zi)} - S(p_j)^{\exp(\beta zi)}) \right),$
where:

- μ_{ij} is 1 if subject i's observed interval encompass the j^{th} Turnbull interval and 0 if this is not the case
- p_j is the right endpoint of the j^{th} Turnbull interval
- z_i is the covariate vector for subject i and β is the corresponding vector of regression coefficients

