Separate summaries are made by severity considering all severe or BG confirmed symptomatic hypoglycaemic episodes, nocturnal severe or BG confirmed symptomatic hypoglycaemic episodes and the ADA classification of hypoglycaemia. All summaries will be prepared for episodes during 26 and 104 weeks of treatment separately.

A negative binomial model with a log-link function and the logarithm of the time period in which a hypoglycaemic episode is considered treatment-emergent as offset will be used to analyse the number of treatment-emergent severe or BG confirmed symptomatic hypoglycaemic episodes during 26 and 104 weeks of treatment. The model will further include treatment, HbA_{1c} group, previous OAD treatment and region as fixed factors.

Number of treatment-emergent nocturnal severe or BG confirmed symptomatic hypoglycaemic episodes during 26 and 104 weeks of treatment will be analysed using the same model as used for the treatment-emergent severe or BG confirmed symptomatic hypoglycaemic episodes.

Clinical evaluation (eye examination, ECG and urine albumin/creatinine ratio)

Eye examination, ECG findings and urine albumin/creatinine ratio will be summarised descriptively, including:

- Summaries for each visit
- Change from baseline after 104 weeks of treatment

Pulse

Change from baseline in pulse will be analysed using the standard MMRM model.

Laboratory assessments (Biochemistry, Haematology and Calcitonin)

All laboratory parameters will be summarised descriptively.

The following tables will be presented:

- Shift tables from baseline to after 26 and 104 weeks of treatment
- Proportion of subjects with measurements outside reference range by treatment and week

Laboratory values will be presented graphically as box plots by treatment and week. For each laboratory parameter, individual values outside the reference ranges (abnormal values) will be listed. Summaries by visit and box plots will be based on data from scheduled visits. If a blood re-sample related to a specific visit is made, the first value will be used.

Shift and outlier tabulations as well as listings will include all recorded values, including values from unscheduled visits

For lipase and amylase the following rule applies in the evaluation of the result:

- If the amylase or lipase baseline (at screening) value is $> 3x$ upper normal range the information will be regarded as medical history for that subject

Classification of Hypoglycaemia

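### The model for the individual 9-point SMPG values leaves out baseline HbA1c group and previous OAD treatment without a stated reason; the cost is modest precision and the fix is one line

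*Protocol*

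**What the plan says.** Section 17.4.1.1 gives the individual profile points an MMRM of their own, with an unstructured residual covariance matrix, and spells out its terms: "The model will include treatment, visit, time, region and treatment by time interaction as fixed factors and baseline value corresponding to each time as covariate". The next sentence adds visit interactions for every factor and covariate. HbA1c group and previous OAD treatment do not appear.

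The other models in Section 17 do use them:

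- Standard MMRM (Section 17): "The model includes treatment, visit, HbA_{1c} group, pre-trial diabetes medication and region as fixed factors". The medication factor is evidently the one defined just below it as previous OAD treatment.
- Profile mean and prandial increments (Section 17.4.1.1): "Change from baseline in mean of the 9-point profile and prandial increment endpoints will be analysed separately using the standard MMRM model".
- HbA1c responder endpoints (Section 17.4.1.1): "logistic regression model with treatment, HbA_{1c} group, previous OAD treatment and region as fixed factors and baseline HbA_{1c} value as a covariate". The composite responder models also name both factors.
- Hypoglycaemic episodes, negative binomial model (Section 17.4.1.2): "The model will further include treatment, HbA_{1c} group, previous OAD treatment and region as fixed factors".
- Primary log-rank test (Section 17.3): "treatment, baseline HbA_{1c} group and previous OAD treatment will be included as strata in the model". The interval-censored proportional hazards model there stratifies on the same two variables.

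On status, Section 4.2.2.1 puts the asterisk on the individual points in the week-26 list only; the week-104 list has none. The footnote explains it: "Key supportive secondary endpoint prospectively selected for disclosure".

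**The concern.** The same nine readings from the same subjects are analysed with two different covariate sets in adjacent paragraphs, and nothing explains why. It does not look like a deliberate simplification, because region was kept. Nor is it a detail left open for the statistical analysis plan: the protocol lists the terms one by one, so a plan that follows it inherits the omission.

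Two things could be at stake. The first is precision at week 26, where the endpoint is key. The second is the missing-data assumption at week 104. Section 17 expects 40% missing for IDegLira and 60% for IGlar, mostly after inadequate glucose control, and relies on missing at random. A baseline factor that predicts both discontinuation and later glucose belongs in such a model.

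**Working it through.** **Inputs from the protocol.** 500 subjects per arm (Section 17.1). Missing data of about 5% at week 26, and 40% and 60% at week 104 (Section 17). Profiles at visits 2, 7 and 13, that is weeks 0, 26 and 104 (Section 8.1.5). Two levels for each omitted factor (Section 17). The protocol gives no SMPG standard deviation, no covariate effect and no power for this endpoint. There is therefore no stated figure to reproduce, and every size below rests on an assumption.

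**Step 1: precision at week 26.** Let R² be the share of residual variance that the two factors explain beyond region and baseline SMPG. Adding them multiplies the standard error by √(1 − R²).

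| Assumed R² | √(1 − R²) | Narrower interval |
|---|---|---|
| 0% | 1.000 | 0% |
| 1% | 0.995 | 0.5% |
| 2% | 0.990 | 1.0% |
| 5% | 0.975 | 2.5% |
| 10% | 0.949 | 5.1% |

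Zero belongs in the range, because each point's own baseline is already in the model and may carry most of what the factors would add. A range of 0% to 5% gives 0% to 2.5%.

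**Step 2: illustration of both visits.** One profile point was simulated with 1,000 subjects, 1,000 replicates, a true difference of −0.50 mmol/L at both visits, and 40% and 60% missing at week 104. Each factor was assumed to shift later glucose by 0, 0.2, 0.4 or 0.6 mmol/L. Where the shift was not zero, the factors also raised the chance of dropout, alongside week-26 glucose. Each data set was analysed with and without the two factors.

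| Shift per factor | Week 26 without / with | Week 104 without / with |
|---|---|---|
| 0 | −0.498 / −0.498 | −0.503 / −0.502 |
| 0.2 | −0.495 / −0.496 | −0.473 / −0.490 |
| 0.4 | −0.500 / −0.501 | −0.467 / −0.502 |
| 0.6 | −0.493 / −0.494 | −0.446 / −0.493 |

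At week 26 the two models agree to within 0.001 in every row, so the contrast is unbiased either way. The empirical standard error at the largest shift is 0.0990 without and 0.0948 with the factors; at zero shift it is 0.1011 and 0.1013, so useless factors cost practically nothing.

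At week 104, omission pulls the estimate toward zero by about 0.03 (0.500 − 0.473 = 0.027) to 0.05 (0.500 − 0.446 = 0.054). With the factors the error is 0.010 or less. The Monte Carlo standard error of a week-104 mean is about 0.15/√1000 = 0.005. The largest bias is 0.054/0.1495 = 0.36 of that scenario's week-104 standard error.

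**Step 3: limits of step 2.** Dropout was generated from terms that the fuller model contains, which favours that model. In the trial, Section 6.4 ties discontinuation to HbA1c at two consecutive visits from week 26. Neither model contains post-baseline HbA1c, so the real repair would be smaller than the table suggests. The simulation also treats one point alone, not the joint nine-point model.

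**Step 4: cost.** Two factors with two levels each and two post-baseline visits give 2 main effects and 2 visit interactions, 4 parameters in all. Expected observations are 1000 × 0.95 = 950 subjects at week 26 and 500 × 0.60 + 500 × 0.40 = 500 at week 104.

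**The case against.** The strongest reply is that nothing here is invalid. The individual points have their own model, and a randomised comparison does not need covariates to be unbiased. Section 11 describes no stratified randomisation, so no randomisation factor goes unadjusted. The gain in precision is small, assumed, and may be zero. All of this stands, and it limits the point to an unexplained inconsistency with a modest cost.

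A reader might infer three stronger things that the documents do not support.

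- *One baseline slope is shared by pre-meal, post-meal, bedtime and 4 am values.* The text speaks of the baseline value belonging to each time, and of covariates in the plural. That is compatible with separate slopes and at most ambiguous; such parameterisation can be left to the statistical analysis plan.
- *Missing at random is harder to defend here than for the profile mean and increments.* The omitted term is baseline HbA1c split at 8.5%, whereas the trigger is post-baseline HbA1c, which neither model holds. If the unstructured matrix spans all times and both visits, the joint model also conditions on all nine week-26 values, which the mean and increment models do not. The comparison could go either way.
- *The gain can be expressed as a number of extra subjects.* Any such figure only restates an assumed R² that may be zero.

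Key status also lends no weight to the week-104 argument, because the individual points are not a key endpoint there.

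**Conclusion.** The point holds as a minor one. The individual-point SMPG model omits two baseline factors that the other regression models in Section 17 adjust for, including those fitted to the same readings, and no reason is given. At week 26, where the endpoint is key, the contrast stays unbiased and the loss is about 0% to 2.5% of interval width, assuming the factors explain 0% to 5% of residual variance beyond baseline SMPG. At week 104, where it is not key, including them may modestly support missing at random if they predict both discontinuation and later glucose. In the favourable illustration above, this was worth up to about 0.05 mmol/L on a difference of 0.50. It cannot fully repair the assumption. The primary analysis and its sample size are not affected.

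**What to change.** In the 9-point profile paragraph of Section 17.4.1.1, add HbA1c group and previous OAD treatment to the fixed factors. The existing sentence on visit interactions then covers them without further change. Use one name for the OAD factor in Section 17 and here. If the omission was intended, one line giving the reason is enough.

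Both factors are already defined for the other models, so no data need to be added. The downside is a few more fixed-effect parameters (4 by the count above), which is negligible for about 950 subjects at week 26 and still small for about 500 at week 104.
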